- b. Amenorrheic for >2 years without a hysterectomy and oophorectomy and a follicle stimulating hormone (FSH) value in the postmenopausal range upon Screening evaluation;
- c. Post hysterectomy, oophorectomy or tubal ligation. Documented hysterectomy or oophorectomy must be confirmed with medical records of the actual procedure or confirmed by an ultrasound. Tubal ligation must be confirmed with medical records of the actual procedure.

12. Have resolution of toxic effect(s) of the most recent prior cancer therapy to Grade 1 or less (except alopecia). If the patient received major surgery or radiation therapy of > 30 Gy, they must have recovered from the toxicity and/or complications from the intervention.

Exclusion Criteria

A patient will not be suitable to proceed to treatment on study if they meet any of the following criteria:

- 1. Has disease suitable for local therapy administered with curative intent.
- 2. Has received more than one prior line of chemotherapy for advanced or metastatic adenocarcinoma of the lung.
For all cohorts: Note: Patients may have received additional prior radiotherapy or chemotherapy in the adjuvant setting, providing it was completed at least 6 months prior to start of study treatment.
- 3. Cohort A: Has received prior therapy with an immunomodulatory agent; Cohort B: Has received prior chemotherapy alone or in combination with immunotherapy in the metastatic setting
- 4. Has a known additional malignancy that is progressing or requires active treatment.
Note: Exceptions include basal cell carcinoma of the skin, squamous cell carcinoma of the skin that has undergone potentially curative therapy or in situ cervical cancer.
- 5. Has known active central nervous system (CNS) metastases and/or carcinomatous meningitis. *Note: Patients with previously treated brain metastases may participate provided they are stable (without evidence of progression by scans (using the identical modality for each assessment, either MRI or CT scan) for at least 4 weeks prior to the first dose of trial treatment and any neurological symptoms have returned to baseline), have no evidence of new or enlarging brain metastases, and are not using steroids for at least 7 days prior to trial treatment.*
- 6. History of the following cardiac conditions:
 - a. Congestive cardiac failure of >Grade II severity according to the NYHA ([Appendix C](#): defined as symptomatic at less than ordinary levels of activity).

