10. Female patients of childbearing potential must have a negative urine or serum pregnancy test within 72 hours prior to the first dose of study treatment. If urine test is positive or cannot be confirmed as negative, a serum pregnancy test will be required.
11. Patients (both male and female) of reproductive potential must be willing to practice highly effective methods of contraception (such as those described in [Section 6.14](#)) throughout the study and for 120 days after the last dose of study medication. Abstinence is acceptable if this is the usual lifestyle for the patient. Female patients are considered NOT of childbearing potential if they have a history of surgical sterility

BerGenBio ASA
[name]
[name]
Norway

or evidence of post-menopausal status defined as any of the following:

- a. ≥ 45 years of age and has not had menses for more than 1 year;
- b. Amenorrheic for <2 years without a hysterectomy and oophorectomy and a follicle stimulating hormone (FSH) value in the postmenopausal range upon Screening evaluation;
- c. Post hysterectomy, oophorectomy or tubal ligation. Documented hysterectomy or oophorectomy must be confirmed with medical records of the actual procedure or confirmed by an ultrasound. Tubal ligation must be confirmed with medical records of the actual procedure.

12. Have resolution of toxic effect(s) of the most recent prior cancer therapy to Grade 1 or less (except alopecia). If subject received major surgery or radiation therapy of >30 Gy, they must have recovered from the toxicity and/or complications from the intervention.

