5.1 Schedule of Study Assessments

This section provides a list of study assessments described by visit. All procedures and assessments should be conducted pre-dose unless otherwise specified. A summary of this information is also provided in Schedule of Study Assessments - [Table 4](#), [Table 5](#) and [Table 6](#) and associated footnotes. Additional assessments may be conducted as clinically indicated.

5.1.1 Schedule of Study Assessments – Year 1, Year 2 and beyond Cycle 35

Screening (up to 28 days prior to Day 1)

- ~ Demographics - gender, ethnicity, race, age (birth month and year)
- ~ Medical history
- ~ Inclusion/exclusion checks
- ~ Pregnancy or FSH test (as appropriate)
- ~ ECOG PS
- ~ Vital signs
- ~ Physical examination
- ~ Clinical chemistry
- ~ Hematology
- ~ Coagulation
- ~ Urinalysis

BerGenBio ASA
[name]
[name]
Norway

- ~ Thyroid function tests
- ~ Echocardiogram (or MUGA)
- ~ ECG (triplicate tests)
- ~ Tumor assessment scans
- ~ Disease Assessment
- ~ Tumor biopsy (fresh tissue mandatory; archival optional)
- ~ Biomarkers
- ~ Concomitant medication

Cycle 1, Day 1 (21-day cycle)

- ~ Vital signs
- ~ Physical examination
- ~ Clinical chemistry
- ~ Hematology
- ~ Coagulation
- ~ Urinalysis
- ~ ECG (triplicate tests; pre-dose and 6 h post bemcentinib dose)
- ~ Biomarkers (if not collected at Screening)
- ~ Pembrolizumab dosing (200 mg fixed dose) - infusion
- ~ Bemcentinib oral dosing [REDACTED]
- ~ PK sampling - bemcentinib [REDACTED] pre-dose, 2, 4, 6 & 8 hours post dose
- ~ PK sampling for storage - pembrolizumab (pre-dose)
- ~ Adverse events
- ~ Concomitant medication

Cycle 1, Day 2

- ~ Vital signs
- ~ Physical examination
- ~ Clinical chemistry
- ~ Hematology
- ~ ECG (triplicate test; pre-dose)
- ~ Bemcentinib oral dosing [REDACTED]
- ~ PK sampling - bemcentinib [REDACTED] (pre-dose)
- ~ PK sampling for storage – pembrolizumab (pre-dose)
- ~ Adverse events
- ~ Concomitant medication

Cycle 1, Day 3

- ~ Vital signs
- ~ Physical examination
- ~ Clinical chemistry
- ~ Hematology
- ~ ECG (triplicate test; pre-dose)

BerGenBio ASA
[name]
[name]
Norway

- ~ Bemcentinib dosing [REDACTED]
- ~ PK sampling - bemcentinib pre-dose, 2, 4, 6 & 8 hours post dose
- ~ PK sampling for storage – pembrolizumab (pre-dose)
- ~ Adverse events
- ~ Concomitant medication

Cycle 1, Day 4

- ~ Vital signs
- ~ Physical examination
- ~ Clinical chemistry
- ~ Hematology
- ~ ECG (triplicate test; pre-dose)
- ~ Biomarkers

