6.14 Contraception

Pembrolizumab and bemcentinib may have adverse effects on a fetus in utero. Furthermore, it is not known if pembrolizumab has transient AEs on the composition of sperm. For this trial, male patients will be considered to be of non-reproductive potential if they have azoospermia (whether due to having had a vasectomy or due to an underlying medical condition).

Female patients will be considered of non-reproductive potential if they are either:

- postmenopausal (defined as at least 12 months with no menses without an alternative medical cause; in women <45 years of age a high FSH level in the postmenopausal range may be used to confirm a post-menopausal state in women not using hormonal contraception or hormonal replacement therapy. In the absence of 12 months of amenorrhea, a single FSH measurement is insufficient.);

OR

- have had a hysterectomy and/or bilateral oophorectomy, bilateral salpingectomy or bilateral tubal ligation/occlusion, at least 6 weeks prior to screening;

OR

- has a congenital or acquired condition that prevents childbearing.

BerGenBio ASA
[name]
[name]
Norway

Female and male patients of reproductive potential must agree to use highly effective methods of contraception while receiving study drug and for 120 days after the last dose of study drug by complying with one of the following highly effective methods[‡]:

- Combined (estrogen and progestogen containing) hormonal contraception associated with inhibition of ovulation:
 - Oral
 - Intravaginal
 - Transdermal
- Progestogen-only hormonal contraception associated with inhibition of ovulation:
 - Oral
 - Injectable
 - implantable
- intrauterine device (IUD);
- intrauterine hormone-releasing system (IUS);
- bilateral tubal occlusion;
- vasectomized partner;
- practice abstinence from heterosexual activity[†]

[†]Abstinence (relative to heterosexual activity) can be used as the sole method of contraception if it is consistently employed as the patient's preferred and usual lifestyle and if considered acceptable by local regulatory agencies and Institutional Review Board (IRB)/Institutional Ethics Committee (IECs). Periodic abstinence e.g., calendar, ovulation, sympto-thermal, post-ovulation methods, etc. and withdrawal are not acceptable methods of contraception.

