16 APPENDIX E: LOCAL LABORATORY PARAMETERS

Clinical Chemistry	Hematology, including Coagulation
Calcium	Red cell count, mean corpuscular volume
Total protein	Hemoglobin
Albumin	Absolute reticulocyte count
Total bilirubin	Platelet count
Alanine transaminase (ALT, SGPT)	White blood cells
Aspartate transaminase (AST, SGOT)	Leucocyte differential count (% & absolute)
Lactate dehydrogenase (LDH)	International normalized ratio or prothrombin time
Alkaline phosphatase	Activated partial thromboplastin time
Glucose (random)	Urinalysis
Sodium	Glucose
Potassium	Protein
Bicarbonate	Bilirubin
Chloride	Ketones
Magnesium	Blood
Urea = Blood urea nitrogen	pH
Creatinine	Specific gravity
Phosphate	Microscopic examination when indicated
Amylase	FSH (female menopausal patients; at Screening)
TSH, Free T4, T3, Free T3	HCG (female pre-menopausal patients; at Screening)

BerGenBio ASA
[name]
[name]
Norway

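### Criterion 11b gives opposite amenorrhea limits in the synopsis and Section 3.1, and neither matches Section 6.14; criterion 9e also differs (minor)

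*Combined protocol and SAP*

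**What the plan says.** Criterion 11 lists the ways in which a woman counts as not of childbearing potential. Item 11b combines a duration of amenorrhea with a postmenopausal-range FSH at Screening. In the synopsis the duration is "Amenorrheic for >2 years without a hysterectomy and oophorectomy". In Section 3.1 it is "Amenorrheic for <2 years without a hysterectomy and oophorectomy", and the rest of the item is the same.

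Section 6.14, which criterion 11 cites for contraceptive methods, has its own definition of non-reproductive potential. Postmenopausal is "defined as at least 12 months with no menses without an alternative medical cause". Under age 45, a high FSH is offered as possible confirmation in women not on hormones. The section adds: "In the absence of 12 months of amenorrhea, a single FSH measurement is insufficient".

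The classification matters because of criterion 10: "Female patients of childbearing potential must have a negative urine or serum pregnancy test within 72 hours prior to the first dose". Section 6.14 gives the reason for caution: "Pembrolizumab and bemcentinib may have adverse effects on a fetus in utero".

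A second difference is in criterion 9e. The synopsis accepts only total bilirubin up to 1.5 times ULN. Section 3.1 also accepts a higher total if direct bilirubin is no more than ULN.

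**The concern.** The two copies of 11b point in opposite directions, and neither states the Section 6.14 limit. Section 3.1 has no lower bound on duration, so it covers amenorrhea of under 12 months backed by one FSH value, which is the situation that Section 6.14 calls insufficient. Nothing in the documents says which text governs.

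At stake is a participant safeguard. A site that screens from Section 3.1 could class such a woman as not of childbearing potential, omit the criterion 10 test, and read the contraception duty as not applying to her. The screening item in Section 5.1.1, a pregnancy test or an FSH test as appropriate, would not by itself alert the site.

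For criterion 9e, the same patient can be eligible under one list and ineligible under the other.

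**Working it through.** The plan gives no figure to reproduce. The check is to classify the same woman under each text. C means of childbearing or reproductive potential, and N means not. The inputs are criteria 11a and 11b in the synopsis and in Section 3.1, and the definition in Section 6.14. Item 11a is the same in both lists: age 45 or over with more than 1 year without menses. Assumptions: intact uterus and ovaries, no hormone use, and no other cause of amenorrhea.

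**FSH in the postmenopausal range**

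| Age | Amenorrhea | Synopsis | Section 3.1 | Section 6.14 |
|---|---|---|---|---|
| Under 45 | under 12 months | C | N | C |
| Under 45 | 12 to under 24 months | C | N | N |
| Under 45 | exactly 24 months | C | C | N |
| Under 45 | over 24 months | N | C | N |
| 45 or over | under 12 months | C | N | C |
| 45 or over | exactly 12 months | C | N | N |
| 45 or over | over 12 months | N | N | N |

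Under 45, the three texts agree at no duration. At 45 or over they differ only up to and including 12 months, because 11a applies after that.

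**FSH not in the postmenopausal range.** Below 12 months all three texts give C at any age. Under 45 with 12 months or more, both copies of criterion 11 give C. Section 6.14 gives C if FSH confirmation is read as required and N if it is read as optional.

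**Which rows matter.** Only the two rows with under 12 months of amenorrhea are unsafe: Section 3.1 gives N where the other two texts give C. In the over-24-month row, Section 3.1 gives C where the others give N, so it demands more precaution than they do.

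**If the Section 3.1 sign is really a greater-than sign.** Section 3.1 then equals the synopsis. Under 45 with a postmenopausal FSH, the classifications (synopsis, Section 3.1, Section 6.14) become C/C/C below 12 months, C/C/N from 12 to 24 months, and N/N/N above 24 months. No unsafe row remains. Criterion 11b is simply stricter than Section 6.14, by 24 − 12 = 12 months.

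**Criterion 9e.** Take a patient with total bilirubin above 1.5 times ULN and direct bilirubin at or below ULN. Section 3.1 admits the patient and the synopsis does not. Appendix E lists total bilirubin but not direct bilirubin, so the test that the Section 3.1 route needs is not in the laboratory list.

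**The case against.** The strongest reply is that the protocol read as a whole still protects this woman.

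- Section 5.3.2 requires a pregnancy test at Screening, and again before each pembrolizumab cycle or at least monthly, in female patients of reproductive potential. Section 6.14 defines that term, and under its definition she is included.
- The contraception duty in criterion 11 is also placed on patients of reproductive potential, and the criterion refers to Section 6.14.
- Footnote 1 to the assessment schedules states a pregnancy test within 3 days before Cycle 1 Day 1, without naming an exempt group.
- Exclusion 34 bars pregnant patients.

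This largely stands. A reader might infer that the protocol releases such a woman from testing and contraception altogether, but the documents do not support that. Appendix E, which lists "HCG (female pre-menopausal patients; at Screening", is an inventory of laboratory parameters and creates no exemption.

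What does not fall away is the wording of Section 3.1 itself. Criterion 10 and 11b exempt her on their face, and a site could treat the single FSH as the confirmation of post-menopausal status mentioned at the end of Section 5.3.2.

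The second reply is that the safety case rests on one character. That is fair. Criterion 9f appears with no comparison sign before 60 mL/min in both lists, so signs in the extracted text are not fully reliable. On the other side, the 30 Gy sign in criterion 12 is the same in both lists. A less-than sign could also be deliberate: time alone in 11a, and a shorter time plus FSH in 11b. The text alone cannot settle it.

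**Conclusion.** Wrong as written, but minor. At least one copy of 11b must be in error, and neither agrees with Section 6.14. The unsafe case is confined to a woman with under 12 months of amenorrhea and one postmenopausal FSH, at a site that relies on the Section 3.1 definition alone. The documents give no count of such women, and few are likely. The unsafe case also assumes that the less-than sign was extracted correctly. If it was not, a mismatch of 24 versus 12 months in the safe direction remains.

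Criterion 9e is a separate matter and is a difference in eligibility, not only in wording. It adds no weight to the 11b point.

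Neither item changes the hypotheses, sample size, error rates or primary analysis of response.

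**What to change.** In both the synopsis and Section 3.1, delete the separate definitions in 11a to 11c. State that a woman is not of childbearing potential when she meets the Section 6.14 definition of non-reproductive potential, and leave Section 6.14 unchanged. This also removes a mismatch in 11c, which accepts oophorectomy or tubal ligation without the bilateral requirement, and surgery without the 6-week interval before screening, that Section 6.14 sets.

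The main downside is that the synopsis limit shortens from 24 to 12 months. Two further details need attention:

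- The instruction in 11c to document prior surgery is not in Section 6.14. If it is wanted, keep it in criterion 11 as a documentation rule.
- FSH confirmation under 45 stays permissive. Making it mandatory would be a separate policy choice that this conflict does not require.

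For criterion 9e, choose one text and use it in both places. If the Section 3.1 text is kept, add direct bilirubin to Appendix E.

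The cost is amendment wording. The 11b change needs no new procedure, because FSH at Screening is already scheduled where post-menopausal status needs confirming. Keeping the Section 3.1 bilirubin text adds one laboratory parameter.

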3.2 Exclusion Criteria

A patient will not be suitable to proceed to treatment on study if they meet any of the following criteria:

1. Has disease suitable for local therapy administered with curative intent.
2. Has received more than one prior line of chemotherapy for advanced or metastatic adenocarcinoma of the lung.
For all cohorts: Note: Patients may have received additional prior radiotherapy or chemotherapy in the adjuvant setting, providing it was completed at least 6 months prior to start of study treatment.
3. Cohort A: Has received prior therapy with an immunomodulatory agent; Cohort B: Has received prior chemotherapy alone or in combination with immunotherapy in the metastatic setting
4. Has a known additional malignancy that is progressing or requires active treatment.
Note: Exceptions include basal cell carcinoma of the skin, squamous cell carcinoma of the skin that has undergone potentially curative therapy or in situ cervical cancer.
5. Has known active central nervous system (CNS) metastases and/or carcinomatous meningitis. *Note: Patients with previously treated brain metastases may participate provided they are stable (without evidence of progression by scans (using the identical modality for each assessment, either MRI or CT scan) for at least 4 weeks prior to the first dose of trial treatment and any neurological symptoms have returned to baseline), have no evidence of new or enlarging brain metastases, and are not using steroids for at least 7 days prior to trial treatment.*
6. History of the following cardiac conditions:
 - a. Congestive cardiac failure of $>$ Grade II severity according to the NYHA ([Appendix C](#): defined as symptomatic at less than ordinary levels of activity).
 - b. Ischemic cardiac event including myocardial infarction within 3 months prior to first dose.
 - c. Uncontrolled cardiac disease, including unstable angina, uncontrolled hypertension (i.e., sustained systolic BP >160 mmHg or diastolic BP

BerGenBio ASA
[name]
[name]
Norway

>90 mmHg), or need to change medication due to lack of disease control within 6 weeks prior to the provision of consent.

- d. History or presence of sustained bradycardia (≤ 55 BPM), left bundle branch block, cardiac pacemaker, or ventricular arrhythmia. *Note: Patients with a supraventricular arrhythmia requiring medical treatment, but with a normal ventricular rate are eligible.*
- e. Family history of long QTc syndrome; personal history of long QTc syndrome or previous drug-induced QTc prolongation of at least Grade 3 (QTc >500 ms).
7. Abnormal left ventricular ejection fraction on echocardiography or Multi Gated Acquisition Scan (MUGA) (less than the lower limit of normal for a patient of that age at the treating institution or $<45\%$, whichever is lower).
8. Current treatment with any agent known to cause Torsades de Pointes which cannot be discontinued at least five half-lives or two weeks prior to the first dose of study treatment.
9. Screening 12-lead ECG with a measurable QTc interval according to Fridericia's correction >450 ms.
10. Is currently participating and receiving study therapy or has participated in a study of an investigational agent and received study therapy or used an investigational device within 4 weeks of the first dose of study treatment.
11. Has participated in a study involving any immune checkpoint inhibitor other than currently approved immune checkpoint inhibitors for their lung cancer.
12. Received chemotherapy or targeted small molecule therapy or radiation therapy within 2 weeks prior to starting study treatment or who has not recovered (i.e., \leq Grade 1 at baseline) from adverse events due to a previously administered agent. *Note: Patients with \leq Grade 2 alopecia are an exception to this criterion.*
If the patient received major surgery, they must have recovered adequately from the toxicity and/or complications from the intervention prior to starting therapy.
13. Received an anti-cancer monoclonal antibody (mAb) within 4 weeks prior to the first dose of study treatment or who has not recovered (i.e., \leq Grade 1 or baseline) from adverse events due to agents administered more than 4 weeks earlier.
14. Major surgery within 28 days prior to start of study treatment and failure to have recovered adequately from the toxicity and/or complications from the intervention prior to the first dose of study treatment. *Note: Major surgery does not include procedures for insertion of venous catheters or biopsies.*
15. Received transfusion of blood products (including platelets or red blood cells) or administration of colony stimulating factors (including G-CSF, GM-CSF or recombinant erythropoietin) within 4 weeks prior to the first dose of study treatment. *Note: Patients receiving stable dose of growth factors with a haemoglobin value that meets Inclusion Criterion 9b may be included.*
16. Has a diagnosis of immunodeficiency or is receiving systemic steroid therapy or any other form of immunosuppressive therapy within 7 days prior to the first dose of study treatment. *Note: The use of physiologic doses of corticosteroids may be approved after consultation with the Sponsor.*
17. Active autoimmune disease that has required systemic treatment in past 2 years (i.e., with use of disease modifying agents, corticosteroids, or immunosuppressive drugs).

BerGenBio ASA
[name]
[name]
Norway

Note: Replacement therapy (e.g., thyroxine, insulin, or physiologic corticosteroid replacement therapy for adrenal or pituitary insufficiency, etc.) is not considered a form of systemic treatment.

18. Known history of human immunodeficiency virus (HIV) (HIV 1/2 antibodies).
19. Has known active infection with Hepatitis B (e.g., HBsAg reactive) or Hepatitis C (e.g., HCV RNA [qualitative] is detected). *Note: i) Patients with a history of hepatitis B infection are eligible provided they are hepatitis B surface antigen negative ii) Patients with a history of hepatitis C infection are eligible provided they have no evidence of hepatitis C RNA using a qPCR at least 6 months after completing treatment for hepatitis infection.*
20. Has received a live-virus vaccination within 30 days of planned treatment start. *Note: Seasonal flu vaccines that do not contain live virus are permitted.*
21. Has a history of (non-infectious) pneumonitis that required steroids or current pneumonitis.
22. Has a history of interstitial lung disease.
23. Inability to swallow or tolerate oral medication.
24. Existing gastrointestinal disease affecting drug absorption such as celiac disease or Crohn's disease, or previous bowel resection which is considered to be clinically significant or could interfere with absorption.
25. Known lactose intolerance.
26. Requires vitamin K antagonists. *Note: Patients receiving low doses prescribed to maintain the patency of venous access devices may be included. Note: Factor Xa antagonists are permitted.*
27. Treatment with any of the following: histamine receptor 2 inhibitors, proton pump inhibitors or antacids within 7 days of start of study.
28. Treatment with any medication which is predominantly metabolized by CYP3A4 and has a narrow therapeutic index.
29. Known severe hypersensitivity (\geq Grade 3) to bemcentinib, pembrolizumab, and/or any of their excipients.
30. Any evidence of severe or uncontrolled systemic conditions (e.g., severe hepatic impairment) or current unstable or uncompensated respiratory or cardiac conditions, or ongoing.
31. Has active infection requiring systemic therapy (apart from cutaneous infections).
32. Has received radiation to the lung of >30 Gy within 6 months of first dose.
33. Has a history or current evidence of any condition, therapy, or laboratory abnormality that might confound the results of the trial, interfere with the patient's participation for the full duration of the trial, or means it is not in the best interest of the patient to participate, in the opinion of the Investigator.
34. Is pregnant or breastfeeding or expecting to conceive or father children within the projected duration of the trial, starting from Screening through to 120 days after the last dose of study treatment.
35. Has known psychiatric or substance abuse disorders that would interfere with cooperation with the requirements of the trial.
36. Cohorts B and C: Has an EGFR mutation or ALK genomic rearrangement.
37. Has received an allogeneic tissue/solid organ transplant.

BerGenBio ASA
[name]
[name]
Norway

